## **Study Design**

This is a prospective, single visit, randomized, double-blind split mouth study.

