## **Study Procedures**

I. All standard of care dental procedures will be followed for enrolled patients except as noted below:

1. IDS will dispense two types of local anesthetic solutionsto dental providers blindly: control solution (non-buffered LA, 2% lidocaine with epinephrine 1:100,000)) and test solution (buffered LA). Both types of solution will be administered to each subject. The types of solutions are labelled with numbers and the research team will remain blind to the type until the study is over.

2. The test solution will be made by a mixing pen called "Onset" (Onpharma Inc., Los Gatos, CA., USA), which is an FDA- approved device (see attachments). IDS will use a cartridge of 2% lidocaine with epinephrine 1:100,000 alkalinized at 9:1 ratio with a resulting pH of 7.21 using 8.4% sodium bicarbonate solution per manufacturer. This mixing pen Onset will deliver 0.18 mL of sodium bicarbonate solution into the anesthetic cartridge.

3. A dental provider will use a randomized coin flip to choose between the blindly labeled anesthetic agents to anesthetize one side of the mouth (left vs right). In addition, the sides of mouth will also be randomly selected by the toss of a coin. After the appropriate blind anesthetic solution has been selected, the same solution will be used to anesthetize each side of the mouth. In general, one cartridge of local anesthetic is sufficient to provide adequate anesthesia for 2 quadrants, however IDS will provide 2 cartridges of each solution in the event that a second cartridge of the same solution is needed. Maximum recommended dosage for local anesthetic will be calculated and followed for each patient. The provider will subsequently anesthetize the opposite side of the mouth with the opposite solution. The sequence used to administer the anesthetic will be inconsequential as the evaluation of pain will remain consistent due to the separation of nerve innervations in the posterior jaw.

4. Two researchers are required to present for each study. One researcher will be the provider who administrates LA and the other will be recording vital signs and physical movements during the injection (see point IV below).

II. In PSU, patients will be monitored per standard of care. This study does not cause potential interference with sedation monitoring.

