III. The only additional device used in this study is Onset mixing system. The Onset device is already FDA-approved for pH buffering dental local anesthetic agents with sodium bicarbonate (see attachments).

IV. Data for this study will come from the EMR, the SDM, and intra-operative data collection sheets.

1. Vital signs, which are already recorded per standard of care at baseline and every 5 minutes, will be recorded manually for significant operative events by researchers on an intra-operative data collection sheet. Significant operative events includes: topical anesthesia, injection (needle puncturing the oral mucosal tissues), delivery of both buffered and conventional local anesthesia, surgical procedures (including tooth preparation, pulpal treatment, and tooth extractions). The necessity of additional local anesthesia delivery will also be noted.

2. Modified Behavioral Pain Scale (BPS) and Pediatric Sedation State Scale (PSSS) are valid and reliable tools in the assessment of pain in the unconscious sedated patient and monitor patient's comfort level during sedation, will be recorded on intra-operative data collection sheet by study personnel during the significant operative events as listed above. We removed the ventilation compliance in BPS form since this is not applicable in our study.

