### **Data Analysis Plan**

To assess compare the changes of vital signs, pain scores between buffered and conventional local anesthesia, we will use independent t-tests (SPSS v25). We considered a P-value of 0.05 or less significant.

The variability in measurements in this dental surgical population is currently unknown, therefore a power analysis is not appropriate. The data from this study will provide the necessary information to perform a power analysis for a future, larger trial.

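### Injection order is dismissed on a local-nerve argument that does not cover whole-body outcomes, and the planned t-test has neither a child nor an order term

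*Combined protocol and SAP*

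**What the plan says.** The Study Design section reads "This is a prospective, single visit, randomized, double-blind split mouth study". Number of Research Participants sets the size at 20 children.

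Under Study Procedures, item I.3, "A dental provider will use a randomized coin flip to choose between the blindly labeled anesthetic agents" for one side of the mouth, and a second toss picks the side. Then "The provider will subsequently anesthetize the opposite side of the mouth with the opposite solution". The same item dismisses order: "The sequence used to administer the anesthetic will be inconsequential as the evaluation of pain will remain consistent". The only reason given is that the nerves on the two sides of the posterior jaw are separate.

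The outcomes are changes in vital signs, physical movement, a modified Behavioral Pain Scale and the Pediatric Sedation State Scale (Objectives; Study Procedures, item IV). On timing, item IV.1 says "Vital signs, which are already recorded per standard of care at baseline and every 5 minutes" and adds manual readings at operative events, which include "delivery of both buffered and conventional local anesthesia, surgical procedures". It does not say which reading a change is measured from.

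The Background section says that a child's reaction to the injection may lead the anesthesiology team to give more sedative.

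The Data Analysis Plan covers the comparison in one sentence: for vital-sign changes and "pain scores between buffered and conventional local anesthesia, we will use independent t-tests (SPSS v25"). It adds: "The data from this study will provide the necessary information to perform a power analysis for a future, larger trial".

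**The concern.** Separate innervation is a sound reason to expect that numbness on one side does not spread to the other. It says nothing about heart rate, blood pressure, respiratory rate, movement or sedation state. These belong to the whole child, and both injections act on them in the same session. By the second injection the child has already had one epinephrine-containing injection and some more time under sedation (the interval is not stated). By the Background section's own account, the child may also have had extra sedative because of the first injection. An order effect is therefore possible, and the stated reason does not exclude it.

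The planned test cannot absorb it. An independent t-test treats the 40 measurements as coming from 40 unrelated children, so it uses neither the pairing nor the order. At stake are the precision of the pilot's comparison, its validity if the first solution changes the response to the second, and the figures passed on to the larger trial.

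**Working it through.** **Inputs from the documents.** 20 children, both solutions in each, one visit; solution chosen by coin flip; the other solution given afterwards; independent t-tests at 0.05. No SD, effect size, order effect or correlation is given, and the plan declines a power analysis, so there is no figure of its own to reproduce.

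**Assumed.** Two-sided testing; the coin-selected solution goes first. The unit is the SD of the within-child difference. The true effect is τ = 0.66, which gives 80% power for a paired t-test with n = 20. ρ is the correlation between a child's two values. π is the amount added to the second response.

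**1. Pure order effect.** A child given buffered second has expected difference (buffered minus control) τ + π; a child given buffered first has τ − π. With n₁ and n₂ children in these two orders, the estimate is shifted by π × (n₁ − n₂)/20. Over coin flips this averages zero, so there is no expected bias. In one trial the split matters (exact binomial, 20 flips):

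- exactly 10:10: 17.6% of trials
- 13:7 or worse: 26.3%, shift at least (13 − 7)/20 = 30% of π
- 14:6 or worse: 11.5%, shift at least (14 − 6)/20 = 40% of π

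**2. Carryover that depends on the first solution.** Let λC be the carryover from control onto a later buffered injection, and λB the carryover from buffered onto a later control injection. The two orders have expected differences τ + π + λC and τ − π − λB. Their average is τ + (λC − λB)/2, so the bias is half the difference in carryover. An order term leaves it unchanged. With τ = −0.66 (buffered better) and λB = 0:

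- λC = −0.5: −0.66 − 0.25 = −0.91 (exaggerated)
- λC = +0.5: −0.66 + 0.25 = −0.41 (shrunk)

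**3. Power.** Simulated 20-child trials with coin-flip order, ρ = 0.5:

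| Order effect π | Planned independent t | Paired t | Paired + order |
|---|---|---|---|
| 0 | 54% | 80% | 77% |
| 0.5 | 51% | 71% | 77% |
| 1 | 44% | 50% | 78% |
| 1.5 | 37% | 33% | 78% |

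At π = 0.5, pairing adds 20 points and the order term about 6 more. At π = 1, pairing adds 6 and the order term 28. At π = 1.5, pairing alone does worse than the planned test. At π = 0.5 with ρ = 0.2 the three figures are 70 / 71 / 78%, and with ρ = 0.8 they are 11 / 71 / 78%.

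**4. Type I error of the planned test.** Write σb for the between-child SD and σe for the within-child SD of one measurement. The true variance of the estimate is (2σe² + π²)/20. The independent test expects about (2σb² + 2σe² + π²/2)/20. The test is conservative while π < 2σb and exceeds 5% beyond that. At ρ = 0.5 the simulated rate is 0.8% at π = 0 and 3.0% at π = 1. At ρ = 0.2 it is 3.0% and 6.7%.

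**5. What reaches the later trial.** Left unadjusted, a pure order effect raises the variance of within-child differences from 1 to 1 + π²: 1.25 at π = 0.5 and 2 at π = 1. Taken alone, that makes the later trial larger. Carryover acts on the effect estimate instead. With |λC| = 0.5 the variance becomes 1 + 0.5²/4 = 1.0625. Sizing on 0.91 gives 1.0625 × (0.66/0.91)² = 0.56 of the required number; sizing on 0.41 gives 1.0625 × (0.66/0.41)² = 2.75 times it.

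**The case against.** The strongest defence is that the coin flip already randomises order, so nothing is biased, and that this is a 20-child pilot with no power claim. For a pure order effect the first half is right, and anyone inferring that the trial is biased by order as such goes further than the documents allow. But randomisation does not deal with carryover that depends on the first solution, and exact balance comes in fewer than one trial in five. The pilot label carries limited weight, because the plan applies a 0.05 threshold and intends to use the data for a later power analysis.

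A second objection is that the missing pairing is the main fault and order is a detail. A reader might infer from the π = 0.5 row that order is always secondary once correlation reaches 0.5. The rows at π = 1 and 1.5 show otherwise: the ranking depends on an order effect nobody knows.

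Third, order may already be captured. Item IV.1 logs each delivery as an event, and item IV draws on the medical record. The list of data to be collected does not name order, but the intra-operative sheet is not in the documents, so one cannot say that order goes unrecorded. What stands is that no analysis of order is planned.

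Fourth, a reader might infer that carryover must flatter the buffered solution, through sedative given after a more painful control injection. The opposite is also conceivable: a painful first injection could leave the child more reactive to the second. The documents support neither sign.

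**Conclusion.** The point holds, as something that should be corrected. The reason given for ignoring order does not reach the outcomes being measured, and the planned test has no child and no order term in a design where each child receives both solutions. A pure order effect gives no expected bias but adds chance imbalance and lost precision. It can also push the planned test's type I error above 5% when it exceeds twice the between-child SD. Differential carryover biases the estimate by half its size, and no order term repairs that.

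The split probabilities and the half-carryover rule follow from the coin-flip design. Every power and error figure rests on assumed values of the effect, the correlation and the order effect, and is illustration only.

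For the later trial, a reader might conclude either that it will merely be larger than needed or that it will be underpowered. Neither can be stated: variance inflation and carryover can pull in different directions, and the plan does not say whether the pilot's effect estimate or only its variability will be used.

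**What to change.** 1. Delete the sentence calling the sequence inconsequential.
2. Replace the independent t-tests with a within-child analysis (paired or mixed model) that has injection order as a fixed effect.
3. Define change from a value recorded just before each injection. Slow drift over the session then largely cancels. The event readings in item IV.1 may already supply this value.
4. Make sure the intra-operative sheet captures order, time of each injection and any sedative given between injections.
5. Report sedative given between injections by first solution, and first-injection results, as descriptive checks. State that the order term does not correct carryover. The first-injection comparison, at 10 against 10, has only about 29% power at correlation 0.5, so it cannot serve as a test.
6. Optionally, have IDS hold a list that balances which solution goes first. Withdrawals may disturb exact balance.

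The cost is one model term and at most three fields on an existing sheet. If there is no order effect, the order term lowers power from 80.0% to 77.5% with coin flips, or by about 0.2 points with a 10:10 split. With coin flips it is a small net loss when the true order effect is below about 0.25 SD; with 10:10 that break-even falls to about 0.1 SD. Carryover bias remains uncorrected either way.

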## **Background**

The ability to manage pain for the pediatric patient during routine dental procedures can have a profound effect on the child's behavior during current and future appointments. Many adults with dental fears and anxiety recall experiencing negative dental experiences during childhood. However, it is difficult to determine whether successful pain management is achieved in children due to their emotional or cognitive developmental levels. Younger children are often unable to provide reliable feedback on a self-reported pain scale when asked to rate their pain perception. The body's response to stress and anxiety during administration of LA can be detected by changes in physiological responses, such as blood pressure (BP), heart rate (HR) and respiratory rate (RR). The anesthesiology team routinely responds to the child's vitals and movements, that if triggered by pain during the injection of a local anesthetic, may lead to administration of additional sedative medications during treatment. Therefore, by monitoring changes in vital signs during the administration of local anesthetic agents may be more reliable to represent the level of pain that a child receives.

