### **Number of Research Participants**

We will enroll 20 children who were patients of the Rainbow Babies and Children's Hospital's (RBC) Tapper Dental Clinic or Dental Clinic of Rainbow Center for Women and Children.

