## **Withdrawal of Research Participants**

Participants could be withdrawn from study without their consent in the event of an error which renders the data yielded inaccurate (for example, monitor malfunction, recording not applied at correct time).

Should participants be withdrawn, their data will be kept but not utilized for the study. All information will be kept in a HIPPA protected file as if they had continued, all privacy maintained in regards to study data.

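### Change in vital signs has no named reference reading; the one stated baseline cancels between solutions, so drift between the two injections stays in each child's difference

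*Combined protocol and SAP*

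**What the plan says.** All references are to the combined protocol and SAP. Objectives and Data Analysis Plan both make change in vital signs an outcome. The analysis sentence reads "To assess compare the changes of vital signs, pain scores between buffered and conventional local anesthesia", using independent t-tests. Neither section gives a reference reading, a time window or a formula.

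Study Procedures IV.1 sets the readings. Vital signs are "already recorded per standard of care at baseline and every 5 minutes, will be recorded manually for significant operative events". The listed events begin with "topical anesthesia, injection (needle puncturing the oral mucosal tissues), delivery of both buffered and conventional local anesthesia" and go on to the surgical steps. Puncture and delivery are therefore separate events, but the moment just before puncture is not an event on either side.

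Study Procedures I.3 chooses the first solution by coin flip, and then: "The provider will subsequently anesthetize the opposite side of the mouth with the opposite solution". No interval between the injections is stated. The same item says: "The sequence used to administer the anesthetic will be inconsequential as the evaluation of pain will remain consistent", giving the separate nerve supply of the two sides as the reason. Item I.4 has a second researcher record vital signs while the injection is given. On size, the plan says "We will enroll 20 children".

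**The concern.** Several planned readings could serve as the reference, and they measure different things:

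- **Session baseline.** There is one per child, so it cannot separate the two sides.
- **Topical anesthesia.** It is not stated to be per side, and its interval to puncture is not given.
- **Routine 5-minute value.** It may be up to 5 minutes old at puncture. If the injections fall close together, one value could serve both sides.
- **Puncture.** It is per injection and precedes any action of the solution, but may already contain the response to the needle.

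With none named, the choice could be made after the data are seen. The nerve-supply argument concerns local anesthesia. Heart rate, respiratory rate and blood pressure are whole-body signs, and both injections act on the same circulation at different times in one sedation. The Background itself describes a way the child's state could shift between them: vital-sign changes and movement, "if triggered by pain during the injection of a local anesthetic, may lead to administration of additional sedative medications during treatment".

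The Data Analysis Plan intends these data to supply the variability for powering a larger trial. The reference reading decides which variability is carried forward.

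**Working it through.** The plan has no power or variance figure to reproduce: 20 children are given without an SD or an effect size.

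**1. Cancellation.** Let B be the session baseline.

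(post_buffered − B) − (post_control − B) = post_buffered − post_control

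B drops out. With complete pairs the difference in group means from the independent t-test is the same quantity. If the second injection is shifted by a mean drift D, each child's difference contains +D or −D according to order.

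**2. Chance imbalance of order.** A simple coin flip in 20 children gives 2 × P(X ≥ 14 | 20, 0.5) = 0.115 for a 14:6 or worse split. At 14:6 the mean shifts by (14 − 6)/20 × D = 0.4 D.

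**3. Precision (assumed model).** Per side, the pre-puncture and post-injection readings share a drift term of SD r and each has independent noise of SD 1. The second injection is shifted by D, order is by coin flip, and there are 20 pairs. The values r = 0.5, 1, 2 and D = 0, 1 are assumptions, in units of noise SD.

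- Variance of the session-baseline difference, per child: 2(1 + r²) + D².
- Effect of D at r = 1: (4 + D²)/4 = 1.06, 1.25, 2.00 for D = 0.5, 1, 2.
- Correlation of pre and post differences, given order: ρ = r²/(1 + r²) = 0.2, 0.5, 0.8, so 1 − ρ² = 0.96, 0.75, 0.36.
- Cost of an order term: the mean of 1/(1 − m²) over coin-flip splits, with m = (2k − 20)/20 for k children given buffered first and all-one-order splits excluded, is 1.06.
- Cost of adding one covariate to that model: 1 + 1/16 = 1.0625. Together: 1.06 × 1.0625 = 1.126.
- Divisor for D = 1: (2(1 + r²) + 1)/(2(1 + r²)) = 1.4, 1.25, 1.1.
- Change score: 4/(2(1 + r²) + D²).

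Variance relative to the session-baseline contrast at the same D:

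| Analysis | D | r = 0.5 | r = 1 | r = 2 |
|---|---|---|---|---|
| Order term only | 0 | 1.06 | 1.06 | 1.06 |
| Reference covariate + order | 0 | 1.08 | 0.84 | 0.41 |
| Change score | 0 | 1.60 | 1.00 | 0.40 |
| Order term only | 1 | 0.76 | 0.85 | 0.96 |
| Reference covariate + order | 1 | 0.77 | 0.68 | 0.37 |
| Change score | 1 | 1.14 | 0.80 | 0.36 |

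Simulations of the same model agree to about 0.01, with null rejection rates of 0.046 to 0.052.

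**4. What the extra reading contributes.** Dividing the covariate-plus-order row by the order-only row gives 1.0625 × (1 − ρ²) = 1.02, 0.80, 0.38, whatever D is. At r = 0.5 the gain under mean drift therefore comes wholly from the order term. The reading pays for itself when ρ² > 1 − 1/1.0625 = 0.0588, that is ρ > 0.243, or r above √(0.243/0.757) = 0.57.

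**5. Puncture reading as reference.** If it carries a needle response of SD s that has gone by delivery and is unrelated to the solution (assumed), the change-score variance at r = 1 and D = 0 is multiplied by (4 + 2s²)/4: 1.125 for s = 0.5 and 1.50 for s = 1. No bias arises.

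**The case against.** The best reply is that a usable reference is already planned. Puncture is listed separately from delivery, so there is a reading on each side before the solution can act, and the needle prick is common to both. Item I.4 favours fresh readings during the injection over copies of an older routine value. This stands in part. It means a new reading is desirable but not indispensable. It does not name the reference, and it does not settle how blood pressure is obtained at the event.

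A second reply is that an order term alone deals with mean drift. That is correct, and the table shows it. It does nothing for drift that varies from child to child, which is where the reference reading helps.

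Stronger readings are tempting, and the documents do not support them:

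- **Bias or false positives.** A reader might infer either from the drift. Order is set by coin flip, so drift unrelated to the first solution averages out over repeated trials. Extra sedation after a painful first injection could distort the size of a real effect, but does not by itself create one under the null.
- **Unusable withdrawal rule.** Its example, "monitor malfunction, recording not applied at correct time", fits the named event recordings and does not depend on a reference reading.
- **Irrecoverable readings.** The plan also draws on the EMR and on a source it calls the SDM. It does not say whether either holds finer readings.

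The argument covers vital signs only. The pain and sedation scales are scored at the events themselves.

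**Conclusion.** The point holds as a gap in outcome definition with a conditional cost in precision. Certain from the text: no reference is named, no reading is required just before puncture on each side, and the one stated baseline cancels if it is used. The sequence argument in I.3 does not cover whole-body signs.

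How much precision is lost depends on drift that the documents do not report. In the assumed model the full remedy ranges from a variance 8% higher (r = 0.5, no mean drift) to about 60% lower (r = 2). Without mean drift it breaks even at r of about 0.7. The need to name the reference remains even if drift is negligible. This should be settled before enrolment, but it does not threaten the validity of the comparison.

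**What to change.** - **Data Analysis Plan:** name the per-side reference reading for change in vital signs. Analyse vital signs within child (buffered minus control) in place of the independent t-test. The primary model has the difference in reference readings as covariate and an order term; the change score is a sensitivity analysis only.
- **Study Procedures IV.1:** where feasible, the researcher already present records heart rate, respiratory rate and blood pressure, with clock time, just before puncture on each side. Otherwise the puncture reading is the named reference.
- **Data collection sheet:** record which solution was given first and whether any sedative was given between the injections.

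The cost is one line per side and two fields on the existing sheet, possibly one extra blood pressure reading per side, and two degrees of freedom (17 instead of 19 in the paired analysis). If drift is small the interval widens slightly: about 4.5% at a ratio of 0.5 without mean drift.
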